4.3 Subject Recruitment, Enrollment and Screening

A maximum total of 17 subjects will be recruited from patients from the Mayo Clinic HIV Clinic and the Hennepin County Medical Center (HCMC). Potential study subjects will be identified and screened for inclusion and exclusion criteria by a member of the study team. Furthermore, other treating clinicians, including residents, fellows and staff physicians, in the Mayo Clinic HIV clinic and HCMC continuity clinic may refer potential study subjects to a study team member. Evaluation and documentation of inclusion and exclusion criteria will be obtained and recorded by an investigator prior to enrollment. Informed consent will be obtained by an MD investigator. Patients will be remunerated for participation in the study (see section 12.3).

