5.2 Treatment Regimen

Patients will be treated in sequential groups after the safety evaluation of each group by the DSMB. Visits 1 and 2 do not have a time window, and can occur without DSMB review as patients will not receive drug at those visits. The following groups will be studied in this protocol:

Group 1: 3 patients with HIV infection, who meet inclusion criteria, will receive ixazomib 1 mg on days 1, 8 and 15 for 28 days. After 28 days, the DSMB will meet to decide if enrollment of the next cohort should proceed. After 84 days (28 days x 3 cycles), the DSMB will meet and decide if patients will receive either (i) ixazomib once weekly for 12 weeks or (ii) ixazomib 1 mg on days 1, 8 and 15 for an additional three 28 days cycles. Visits 3-15 will have a window of \pm 3 days.

Group 2: 3 patients with HIV infection, who meet inclusion criteria, will receive ixazomib 2 mg on days 1, 8 and 15 for 28 days. After 28 days, the DSMB will meet to decide if enrollment of the next cohort should proceed. After 84 days (28 days x 3 cycles), the DSMB will meet and decide if patients will receive either (i) ixazomib once weekly for 12 weeks or (ii) ixazomib 2 mg

on days 1, 8 and 15 for an additional three 28 days cycles. Visits 3-15 will have a window of ± 3 days.

[figure not shown]
Group 3: 3 patients with HIV infection, who meet inclusion criteria, will receive ixazomib 3 mg on days 1, 8 and 15 for 28 days. After 28 days, the DSMB will meet to decide if enrollment of the next cohort should proceed. After 84 days (28 days x 3 cycles), the DSMB will meet and decide if patients will receive either (i) ixazomib once weekly for 12 weeks or (ii) ixazomib 3 mg on days 1, 8 and 15 for an additional three 28 days cycles. Visits 3-15 will have a window of ± 3 days.

Group 4: 3 patients with HIV infection, who meet inclusion criteria, will receive ixazomib 4 mg on days 1, 8 and 15 for 28 days. After 28 days, the DSMB will meet to decide if enrollment of the next cohort should proceed. After 84 days (28 days x 3 cycles), the DSMB will meet and decide if patients will receive either (i) ixazomib once weekly for 12 weeks or (ii) ixazomib 4 mg on days 1, 8 and 15 for an additional three 28 days cycles. Visits 3-15 will have a window of ± 3 days.

Group 5: 5 patients with HIV infection, who meet inclusion criteria will receive the maximum tolerated dose of ixazomib as determined by DSMB recommendation. Visits 3-15 will have a window of ± 3 days.

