5.3 Method for Assigning Subjects to Treatment Groups

Each group (or dose level) will enroll and after 4 weeks of follow up of 3 patients treated with ixazomib at a particular dose will be reviewed for safety by DSMB before initiating enrollment into the next group (or dose level). All patients in the current cohort must have completed 4 weeks and the cohort's data reviewed by the by the Safety Monitoring Committee before patients in the next cohort can receive drug. Patients from the next cohort may complete the first two visits prior to DSMB review of earlier cohorts.

Dose limiting toxicities are defined in Section 6.17 Table 2. After all the subjects in each dosing group has completed Cycle 1 of ixazomib, the DSMB may recommend:

- (i) Proceed to next dose level, or
- (ii) Terminate trial, or
- (iii) Enroll a replacement subject for a withdrawn subject, or
- (iv) Add 5 more patients at previous dose group (maximum tolerated dose). The maximum tolerated dose is that level where no more than 0 out of 3 patients experience dose limiting toxicity.

If no DLT are observed in 3 subjects, the next dosing level will be initiated.

After DSMB review of the 4 mg dosing level, if no DLT are observed, the DSMB may recommend:

- (i) Terminating the trial
- (ii) Enroll 5 more patients at the maximum tolerated dose.

The NNRTIs etravirine and efavirenz are moderate CYP3A enzyme inducers and have potential to decrease systemic exposure to ixazomib. That possibility will be explored by measuring trough ixazomib levels in all patients and comparing ixazomib concentrations in patients on different ART regimens. The DSMB will have to consider the number of patients treated with NNRTIs in a particular group as the safety profile of a group may be underestimated if the majority of patients are treated with NNRTIs as part of their ARV regimen.

Additional data review by the DSMB will occur after Day 84 for each dosing cohort. At this time, the DSMB may recommend:

[figure not shown]
- (i) Proceed to uninterrupted weekly dosing on days 1, 8, 15 and 22 of a 28 day cycle, or
- (ii) Continue previous dosing on days 1, 8, and 15 of a 28 day cycle, or
- (iii) Enroll a replacement subject for a withdrawn subject, or
- (iv) Terminate dosing.

This determination will be made on an individual participant basis, and not a dosing cohort basis, and will be made based on the presence or absence of adverse drug effects that do not meet the definition of dose related toxicities.

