6.16 Table 1. Table of Study Activities

Study Activity	V 1	V 2	V 3 ^c	V 3.5	V 4	V 5	V 6	V 7	V 8	V 9	V 10	V 11	V 12	V 13	V 14	V 15
Eligibility Screening	X															
Peripheral Neuropathy self-reported questionnaire	X		X		X	X	X	X	X	X	X	X	X		X	X
Informed consent	X															
Medical History	X		X		X	X	X	X	X	X	X	X	X		X	X
Concurrent meds	X															
Complete physical exam	X															
Brief physical exam			X		X	X	X	X	X	X	X	X	X		X	X
Vital Signs	X		X		X	X	X	X	X	X	X	X	X		X	X
CD4/CD8 T cell counts	X						X	X		X	X	X	X		X	X
HIV RNA Viral load	X							X		X	X	X	X		X	X
HIV Proviral DNA	X							X		X	X	X	X		X	X
CBC w/diff, platelet ^a	X		X		X	X	X	X	X	X	X	X	X	X	X	X
Heparin tubes for PBMC and plasma storage	X		X	X				X		X	X	X	X		X	
Serum chemistry ^b	X					X		X	X	X	X	X	X		X	X
Pre- and post-dose ixazomib level									X					X		
Adverse event evaluation					X	X	X	X	X	X	X	X	X		X	X
Urine Pregnancy test	X															
Leukapheresis		X												X		

a – Increased blood draw frequency may be required in the presence of hematologic toxicity. This will occur prior to each dose of ixazomib. In addition, increased blood draw frequency may be required if ixazomib is dosed weekly uninterrupted in Cycles 4-6.

b - Potassium, Creatinine, Alkaline phosphatase, ALT, AST, Total bilirubin, Direct bilirubin, Sodium, BUN, glucose, Chloride, Bicarbonate.

c- Visits 1 and 2 can occur on the same date, as long as they occur before visit 3.

6.17 Table 2: Instructions for treatment delays and dose reductions prior to ixazomib administration

CTCAE System/Organ/Class (SOC)	ADVERSE EVENT	AGENT	ACTION**
BASED ON INTERVAL ADVERSE EVENT			

CTCAE System/Organ/Class (SOC)	ADVERSE EVENT	AGENT	ACTION**
Investigations	Grade 2 thrombocytopenia (PLT count <75,000 - 50,000/mm ³) and/or neutropenia <1500 - 1000/mm ³	Ixazomib	Ixazomib dose should be omitted until the PLT and/or ANC has recovered to baseline values (counts >lower limit of normal). Ixazomib may be reinitiated at the same dose if the recovery has occurred in less than 7days. If the abnormality lasts ≥7 days or recurs, then the dose of ixazomib should be reduced by one dose level. If a patient is already at the lowest dose level, ixazomib should be permanently discontinued. Patients should have CBC checked weekly until resolution of abnormality.
	≥Grade 3 thrombocytopenia and/or neutropenia		Permanently discontinue ixazomib

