7.2 Statistical Methods

Descriptive Statistics

Univariate descriptive statistics and frequency distributions will be calculated, as appropriate for all variables. Baseline values for demographic, clinical, and outcome variables will be tabulated for the treatment groups. These analyses will help identify potential confounding variables to be used as covariates in sensitivity analyses. Putative prognostic variables that will be investigated through these descriptive analyses include variables such as age, sex, race/ethnicity, and duration of HIV infection, baseline CD4 T cell count and HIV viral load, mode of transmission, duration of ART, and duration of viral suppression.

Multiplicity

No *a priori* correction to the type I error rate is warranted for this study.

Primary Analysis

Ixazomib will be safe and well tolerated in HIV positive persons on suppressive ART.

Description statistics will be used to describe the rates of adverse effects by CTC grade of ixazomib among the dosing groups.

Secondary Analysis 1:

Ixazomib will reduce HIV DNA and replication competent viral reservoir size and improve CD4 T cell counts in HIV positive patients on suppressive ART.

To test this hypothesis, a mixed model will be estimated for each outcome separately. This model will consider linear trajectories and more flexible distribution of outcomes over time using each assessment point as a factor (i.e., a “repeated measures ANOVA formulation”). Given the limitations of the sample size, random effects for only subject (random intercept) models will be considered. These models will examine the treatment by time interaction and the linear trajectory model will be expected to have greater, but relatively poor, power to detect differences in outcomes such as viral load over time. An alpha of 0.1 or lower will be considered sufficiently significant to serve as preliminary evidence of a biologic effect to warrant further studies.

In the event the models are not able to be estimated from the data available, a planned post-hoc analysis will compare changes in secondary endpoints between participants on integrase inhibitor-based ART and non-nucleoside reverse transcriptase-based ART.

Interim Analysis

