7.3 Subject Population(s) for Analysis

The per-protocol analysis set will be of participants followed according to the study schedule. This subset of the entire study sample will be of particular interest to the mechanistic studies since all data will be available. The results of this potentially non-representative subset will be compared to the results obtained using the Safety Evaluable Analysis Set as a sensitivity analysis. Should the results disagree qualitatively, the ITT results will be considered the less-biased results; however, a careful examination of putative causes for the differences will be fully investigated to inform a Phase II/III confirmatory study.

The Safety Evaluable Analysis Set will consist of all participants that have at least one dose of study medication. This analysis set will serve as the basis for the primary analysis noted above and adverse event reporting of treatment emergent and/or worsening events.

8 Safety and Adverse Events

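### The 24-week adverse-event table by dosing group may pool different doses and schedules, and cannot show the safety of the uninterrupted weekly schedule

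*Combined protocol and SAP*

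**What the plan says.** Safety and tolerability are the primary endpoint (Section 3.2). The method in Section 7.2 is: "Description statistics will be used to describe the rates of adverse effects by CTC grade of ixazomib among the dosing groups". Section 7.3 adds the population: "The Safety Evaluable Analysis Set will consist of all participants that have at least one dose of study medication". Neither section says how an AE is attributed once a patient's dose or schedule has changed.

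The only dosing groups defined are the enrolment cohorts of Section 5.2. The first reads "Group 1: 3 patients with HIV infection, who meet inclusion criteria, will receive ixazomib 1 mg on days 1, 8 and 15 for 28 days", and Groups 2 to 4 follow the same pattern at 2, 3 and 4 mg. The five patients in Group 5 "will receive the maximum tolerated dose of ixazomib as determined by DSMB recommendation". Section 4.3 caps the total: "A maximum total of 17 subjects will be recruited".

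Two provisions let exposure vary within a cohort:

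- **Schedule.** After Day 84 the DSMB's options in Section 5.3 include "Proceed to uninterrupted weekly dosing on days 1, 8, 15 and 22 of a 28 day cycle" or staying on days 1, 8 and 15. Section 5.3 adds: "This determination will be made on an individual participant basis, and not a dosing cohort basis". The criterion is whether the patient has had adverse drug effects short of a dose-limiting toxicity.
- **Dose.** Under Table 2 (Section 6.17), if a Grade 2 cytopenia or a liver-test rise of Grade 2 or more is prolonged or recurs, "then the dose of ixazomib should be reduced by one dose level". A recurrent rash of Grade 2 or lower also leads to a one-level reduction.

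**The concern.** A cohort label fixes the planned exposure for the first three cycles only. After that, two patients with the same label may be on different schedules, and a patient reduced under Table 2 may be on another cohort's dose. The changes also depend on the outcome being tabulated: patients who tolerate the drug may receive more of it, and some with toxicity receive less.

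Three things are at stake in the 24-week table. AEs on the uninterrupted weekly schedule have no row of their own. AEs on a reduced dose may be read as AEs on the cohort dose. And without an exposure denominator, a patient who took 21 doses counts the same as one who stopped early.

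The protocol itself treats the weekly schedule as relevant to safety monitoring: footnote a to Table 1 (Section 6.16) allows more frequent blood draws for patients on it in Cycles 4-6. Laboratory AEs may then be detected more often on that schedule, which is a further reason to show it separately.

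**Working it through.** **The plan's own figure.** Groups 1 to 4 with 3 patients each, plus 5 in Group 5: 4 × 3 + 5 = 17, matching Section 4.3. Section 7.1 bases the sample size on recruitment, and the primary analysis is descriptive, so there is no power figure to reproduce.

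**Planned doses (Sections 5.2 and 5.3).** Treatment lasts 6 × 28 days = 24 weeks.

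| Course | Weeks 1-12 | Weeks 13-24 | Total |
|---|---|---|---|
| Days 1, 8, 15 throughout | 3 × 3 = 9 | 3 × 3 = 9 | 18 |
| Weekly from Day 84 | 9 | 12 | 21 |

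The difference is 21/18 − 1 = 16.7% overall and 12/9 − 1 = 33.3% in Weeks 13-24.

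**Spread within one cohort, in mg.** Option (i) in Section 5.2 states no mg amount for weekly dosing. *Assuming* it keeps the group dose, a Group 4 patient who completes treatment takes 18 × 4 = 72 mg or 21 × 4 = 84 mg. A patient reduced from 4 to 3 mg after Cycle 1 and kept on days 1, 8 and 15 takes 3 × 4 + 15 × 3 = 57 mg. On the same assumption, 3 mg weekly and 4 mg on days 1, 8 and 15 give equal amounts in Weeks 13-24 (12 × 3 = 9 × 4 = 36 mg) under different labels.

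**How a schedule effect would appear (assumed risks).** Let *p* be the AE risk in Weeks 13-24 on days 1, 8 and 15, *q* the risk on weekly dosing, and *k* the number of the 3 patients on weekly dosing. The expected cohort rate is [*kq* + (3 − *k*)*p*]/3.

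| *p*, *q* | *k* = 0 | 1 | 2 | 3 |
|---|---|---|---|---|
| 10%, 30% | 10.0% | 16.7% | 23.3% | 30.0% |
| 20%, 40% | 20.0% | 26.7% | 33.3% | 40.0% |
| 20%, 60% | 20.0% | 33.3% | 46.7% | 60.0% |

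With the risks held fixed, the cohort rate moves only with *k*, which the planned table does not show.

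**How a dose effect would appear (assumed rates).** Take 0.20 AEs per patient-cycle at 4 mg and 0.10 at 3 mg, with *r* of 3 Group 4 patients reduced after Cycle 1. The cohort has 3 × 6 = 18 patient-cycles, so the rate is [(18 − 5*r*) × 0.20 + 5*r* × 0.10]/18. This gives 0.172, 0.144 and 0.117 for *r* = 1, 2 and 3, against 0.20 at 4 mg. With 0.30 and 0.10 the figures are 0.244, 0.189 and 0.133.

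**Limit on precision.** The exact 95% upper limit for 0/3 is 1 − 0.025^(1/3) = 70.8%; the interval for 1/3 is 0.8% to 90.6%. One patient is 33 percentage points in a cohort of 3 and 20 points in Group 5. Better attribution does not make these rates precise.

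**What is recorded.** Section 8.3.1 lists the AE date among the worksheet fields but neither dose nor schedule at onset. Section 5.8.3 keeps strength, quantity and dispensing date.

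**The case against.** - **Attribution by assigned dose is an inference.** A reader might infer that the plan has chosen to count every AE under the assigned dose for 24 weeks. Section 7.2 names only the dosing groups. The cohort reading follows from Section 5.2 and from the absence of any other rule. The DSMB charter in Section 9.4.1, with its own safety analysis plan, is not in the documents and may contain a rule, though it would not replace the text of the primary analysis.
- **The changes are conditional.** A reader might infer that after Week 12 the label no longer describes what patients take. The DSMB may leave the schedule unchanged, Table 2 reductions need specific events, more serious toxicity generally leads to discontinuation, and Group 1 has no lower level. The label may stop describing exposure; how often is unknown.
- **Escalation is not compromised.** It rests on the review after 4 weeks (Sections 5.3 and 7.2), before any schedule choice. A reader who infers that the maximum tolerated dose is undermined goes beyond the documents.
- **A table by actual exposure has its own bias.** Weekly dosing is given on the basis of earlier tolerability, so a raw schedule comparison can make it look safer. With a half-life of 3.6 to 11.3 days (Section 1.5), an AE soon after a reduction may reflect the previous dose. The cohort table does not condition on tolerability and should not be demoted.
- **The first 12 weeks are not perfectly uniform.** Table 2 reductions can occur then, and Section 5.2 does not state Group 5's schedule.

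All of these stand as limits. They do not answer the central gap: as written, nothing in the table describes AEs on the uninterrupted weekly schedule.

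**Conclusion.** The point holds as a cheap improvement. The cohort table may combine courses of 18 and 21 planned doses, and doses lowered individually, without showing it. The dose counts follow from the documents. The mg comparisons hold only if weekly dosing keeps the group dose, which the Study Summary and Section 5.2 do not state. The dilution figures rest on assumed AE risks and show a mechanism; they do not predict its size. A reader might infer that the table will flatten any dose-toxicity relation. It could, but with 3 patients per cohort neither tabulation can establish or exclude such a relation, and no figure in the documents supports the stronger statement.

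**What to change.** Amend Section 7.2 as follows:

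1. Keep the table by enrolled group, but report Weeks 1-12 and Weeks 13-24 separately. Base the between-dose description on Weeks 1-12, and note any Table 2 reductions in that period.
2. Beside it, add a table or by-patient listing of AEs by actual dose in mg and schedule at onset. Give patients and doses or patient-weeks at risk, and the time since any dose change. Pool Group 5 with the earlier group on the same dose, since a table by group number would separate them.
3. Add dose and schedule at onset to the AE worksheet in Section 8.3.1.
4. State that the Weeks 13-24 comparison of schedules is selected on earlier tolerability and is descriptive only.

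The cost is a few sentences, two worksheet fields and one or two tables, drawing on AE dates and dispensing records already kept. Sample size and treatment do not change. The drawback is small cells in Weeks 13-24; with at most 17 patients, a by-patient listing may be the more readable form.

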Next, we wanted to test whether the reactivating cells were in fact the cells that died in response to treatment. We treated cells from two ART-suppressed HIV-infected patients with bortezomib or ixazomib in the presence of anti-retroviral drugs to prevent spreading infection, and analyzed cells for the co-expression of caspase 3 (as a marker of apoptosis) and p24 (as a marker of reactivation) (Figure 10B and 10C). In cells that stained positive for p24, low and high dose bortezomib increased the proportion of caspase 3-positive cells from 17% (control) to 24% (5 nM bortezomib) and 60% (10 nM bortezomib); however bortezomib also increased the proportion of HIV p24 positive cells that were caspase 3 positive, suggesting nonspecific toxicity, consistent with bortezomib causing leukopenia in a significant proportion of patients (74). In the case of ixazomib, treatment with 100 nM of the drug resulted in a significant increase in the proportion of caspase 3-expressing p24-positive cells (27% vs 17% in controls, $p = 0.023$), while not significantly increasing the proportion of p24 negative cells that stain for active caspase 3, suggesting limited nonspecific toxicity, and consistent with the recent phase three trial data using ixazomib in myeloma patients, in which the rate of all side effects including leukopenia were not different between placebo and Ixazomib treatment arms. (Figure 10B and C).

There is considerable debate about which is the best technique available to estimate HIV reservoir size (75). Highly sensitive nucleic acid amplification techniques have been developed which can accurately detect low copy number HIV genes with a very low coefficient of variance, such as a digital droplet PCR (ddPCR) (76). However, such approaches cannot distinguish replication-competent from replication-incompetent (defective) virus (77), the latter being estimated to represent ~80 % of detectable viral sequences. On the other hand, functional assays such as the quantitative viral outgrowth assay (QVOA) are specific for replication-competent virus, but they underestimate the size of the latent pool (69, 78, 79), and are infrequently positive in cells from ART-suppressed patients. Thus, we opted to estimate HIV reservoir size *ex vivo* using the more sensitive approach – ddPCR – with the understanding that any reduction in HIV DNA would confer at least a similar degree of reduction in replication competent virus.

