In our first series of experiments, we established and validated ddPCR, as follows. Cell-associated HIV polymerase copies were measured repeatedly over 10 different runs in positive control samples containing a fixed ratio of uninfected Jurkat T cells and chronically HIV-infected 8E5 T cells, which contain one integrated HIV provirus per cell. We were able to obtain a coefficient of variance of ddPCR of 3.8% (Figure 10D), thereby enabling us to interpret changes of greater than 3.8% as being greater than the noise of the assay. Next, 37 HIV-negative samples were assayed for cell-associated HIV polymerase, establishing a detection limit of 45 HIV DNA copies per million cells (Figure 10E).

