Next we assessed changes in cell-associated HIV DNA in primary CD4⁺ T cells from ART-suppressed HIV patients, following maximal HIV reactivation by α CD3/ α CD28 in the presence or absence of bortezomib or ixazomib. First, we isolated CD4⁺ T cells from cryopreserved leukapheresis PBMC samples from 6 individual ART-suppressed HIV patients, and pre-treated with bortezomib or ixazomib for 24 hours prior to viral reactivation with α CD3/CD28 stimulation. Total cell-associated HIV DNA was measured by ddPCR 72 hours after reactivation. Treatment with bortezomib followed by reactivation did not reduce HIV DNA in the leukapheresis samples (Figure 10F left panel), whereas ixazomib followed by viral reactivation resulted in a geometric mean 31% reduction ($P=0.06$) in HIV DNA when compared with reactivation alone (Figure 10F right panel). We next treated freshly obtained primary CD4 T cells from 12 ART suppressed patients with ixazomib or vehicle control prior to reactivation with α CD3/28 as above. Cells from 8 of 12 patients treated with ixazomib had a decrease in cell associated HIV DNA of $\geq 10\%$ compared to control, and were considered treatment responders. In these responders ($N=8$), ixazomib reduced cell associated HIV DNA by a geometric mean of 44% ($P=0.002$) compared to control treated cells (Figure 10G). We next focused on whether treatment of cells from an additional 11 HIV-infected, ART-suppressed patients with ixazomib alone would be sufficient to both reactivate HIV and prime the cells towards an apoptosis-prone phenotype, so as to result in a reduction in cell-associated HIV DNA content when used as monotherapy, in the setting of continued ART. Treatment of CD4⁺ T cells with ixazomib (100nM) alone for 96 hours without additional reactivation stimuli reduced cell associated HIV DNA by a geometric mean 37% compared to vehicle treated cells ($P=0.02$, data not shown).

[figure not shown]
[figure not shown]

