- Culturable HIV – replication competent latent viral reservoir will be estimated using a quantitative viral outgrowth assay, considered the gold standard measurement, on peripheral blood CD4 T cells from baseline and post-treatment leukapheresis samples ([name] HIV Laboratory).

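### The mixed model for culturable HIV has no stated scale or rule for non-detects, so the estimated change would depend on an unstated substitution

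*Combined protocol and SAP*

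**What the plan says.** Section 7.2, Secondary Analysis 1, covers HIV DNA, the replication-competent reservoir and CD4 counts together: "a mixed model will be estimated for each outcome separately". It adds that "random effects for only subject (random intercept) models will be considered" and offers time either as a linear trend or as a factor. "An alpha of 0.1 or lower will be considered sufficiently significant" to count as preliminary evidence that justifies further studies. If the models cannot be estimated, the fallback compares patients by class of antiretroviral regimen.

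On the assays:

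- Section 1.1 says that viral outgrowth assays "are infrequently positive in cells from ART-suppressed patients". Section 4.1 requires suppressed viral load, so this is the trial's population.
- Section 6 makes this assay a trial outcome: "replication competent latent viral reservoir will be estimated using a quantitative viral outgrowth assay, considered the gold standard measurement". It is run on the baseline and post-treatment leukapheresis samples.
- Section 1.1 describes validation of ddPCR, "establishing a detection limit of 45 HIV DNA copies per million cells". Section 6 also makes ddPCR a trial outcome.

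Nowhere do the documents give a transformation, an error distribution, a censored likelihood or a substitution rule for any of these outcomes.

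**The concern.** The sponsor knows that the outgrowth assay is often negative in these patients but does not carry this into the analysis. A linear mixed model needs a number for every sample. A negative culture supplies only an upper bound, so someone must choose a value or drop the sample. With no rule in the plan, that choice can be made after the results are seen.

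At stake is the signal that Section 7.2 uses to decide whether further work is warranted. A real fall could be reported as no effect, or the reported size could reflect the substituted constant rather than the drug. The fallback gives no protection: it addresses a different question, and a model with substituted values will usually still fit.

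**Working it through.** The documents state no power, SD, expected effect or positivity rate, so there is no planned figure to reproduce. What follows is a range under stated assumptions.

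**Inputs from the documents.** At most 17 patients (Study Summary; 4 × 3 + 5 = 17). Two leukapheresis time points (Section 6). Alpha 0.1, sidedness not given (Section 7.2). For the size of a plausible effect I used the ex vivo result that ixazomib alone "reduced cell associated HIV DNA by a geometric mean 37% compared to vehicle treated cells" (Section 1.1). It is not a planned trial effect. On the log10 scale it is log10(0.63) = −0.2007.

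**Assumed.** Normal log10 values with total SD s = 0.5; within-patient correlation r of 0.9, 0.75 or 0.64 (within-patient SD 0.5 × √(1 − r) = 0.16, 0.25 or 0.30); baseline positivity p from 20% to 80%; a common fall in all 17 patients.

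**Step 1: expected estimate.** Put the limit at 0. The baseline mean is m0 = s·Φ⁻¹(p), and the post-treatment mean is m1 = m0 − 0.2007. If non-detects are set to the limit, the expected value at mean m is E(m) = m·Φ(m/s) + s·φ(m/s), and the expected change is E(m1) − E(m0). If they are set k log10 units lower, add k·(q − p), where q = Φ(m1/s) is post-treatment positivity.

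At p = 0.4: m0 = −0.1267, m1 = −0.3273, q = 0.2563, E(m0) = 0.1425 and E(m1) = 0.0771.

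- At the limit: 0.0771 − 0.1425 = −0.0654, a fall of 1 − 10^(−0.0654) = 14%.
- Half the limit (k = 0.3010): −0.0654 − 0.3010 × 0.1437 = −0.1087, a fall of 22%.
- One tenth (k = 1): −0.0654 − 0.1437 = −0.2091, a fall of 38%.

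| Baseline positivity | Limit | Half the limit | One tenth | True |
|---|---|---|---|---|
| 20% | 7% | 12% | 25% | 37% |
| 40% | 14% | 22% | 38% | 37% |
| 60% | 21% | 30% | 45% | 37% |
| 80% | 29% | 35% | 47% | 37% |

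These expectations do not depend on r. Simulation of 20,000 trials per setting agrees to within a percentage point.

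Two other rules were tried with between-patient SD 0.5 and within-patient SD 0.3, at 20%, 35% and 50% positivity. Dropping non-detects gave 16%, 15% and 21%. Zeros on the raw scale gave 47%, 42% and 43%, against 34% to 38% for the uncensored ratio of means.

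**Step 2: power at n = 17.** With complete data at two time points, the time effect of the random-intercept model is the paired t-test. At two-sided 0.1:

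- r = 0.9, limit substituted, positivity 20/40/60/80%: 25/62/82/92%, against 97% uncensored. On average 13, 10, 6 and 3 of the 17 pairs show exactly zero change.
- r = 0.75, same rule: 17/39/53/64%, against about 73%.
- r = 0.64, positivity 20%: about 15% (limit), 23% (half) and 24% (one tenth), against 59%.

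**Step 3: a left-censored random-intercept model.** In large samples it returned 37% to 38% in every setting. At n = 17 it recovered 35% to 38%. At 20% positivity and r = 0.9 its power was 57%, against 25% for limit substitution. Its one-directional type I error reached about 0.12 in places, against a nominal 0.05, so part of that gain is not real.

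**Step 4: ddPCR.** Limit 45 copies per million, between-patient SD 0.5, within-patient SD 0.2 (assumed):

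| Baseline, copies per million | Limit | Half | Dropped | One tenth |
|---|---|---|---|---|
| 100 | 26% | 33% | 28% | 46% |
| 300 | 35% | 37% | 35% | 42% |

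At 1,000 or more, at least 98% of values are detected, and the first three rules are off by no more than about one percentage point.

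**The case against.** Several points on the other side stand.

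- **Direction.** A reader might infer that any substituted constant understates the fall. The working shows otherwise: one tenth of the limit overstates it at 60% and 80% positivity, and raw-scale zeros overstate it too. The documents fix no rule, so they fix no direction.
- **What the plan chose.** A reader might infer that the plan specifies a Gaussian model with substitution. The repeated-measures wording makes a linear model the likely reading, but the defect is silence on scale and non-detects.
- **ddPCR.** A reader might infer that two of the three secondary objectives are equally affected. The documents give no baseline HIV DNA level and report no non-detects in the patient-cell experiments. The 45-copy limit comes from preliminary validation; nothing says that it carries over to the trial's ddPCR system or to CD4 subsets.
- **Positivity.** The background remark gives no rate, and it was made to explain the choice of assay for ex vivo work. The trial uses leukapheresis samples.
- **Power.** The figures depend heavily on an undocumented correlation. No analysis could reach the uncensored comparator, because censoring itself loses information.
- **Stakes.** These are secondary outcomes in a pilot sized by recruitment, and Section 7.2 already expects relatively poor power.

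These points narrow the concern mainly to culturable HIV and to an undetermined estimate. They do not supply the missing rule.

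**Conclusion.** The point holds for culturable HIV. Section 7.2 applies a model that cannot use a negative assay without an extra rule, gives no such rule, and does so for an assay that the protocol calls infrequently positive in this population. At 20% to 60% positivity, the common substitutions (the limit or half of it) turn a true 37% fall into about 7% to 30%. A very low constant can exaggerate the fall once positivity is moderate. At 40% positivity the same data give 14% or 38% depending on the constant alone. Power fell under every constant tried.

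The sizes rest on assumed positivity, SDs, correlation and a common effect across doses. That the estimate depends on the rule follows whenever non-detects are not rare. For ddPCR the point is conditional: it matters if baselines lie at about 100 to 300 copies per million and is negligible at 1,000 or more. The primary safety analysis is untouched.

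**What to change.** Add to Section 7.2:

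- **Culturable HIV.** Model the positive and negative wells with cells plated per well in a limiting-dilution likelihood: complementary log-log link, log cell-input offset, patient random effect and time effect. The alternative is log10 values in a left-censored mixed model. Calibrate inference by permutation or bootstrap, because asymptotic tests can be anticonservative at n = 17.
- **Sensitivity.** Report the estimate over a stated set of substituted values.
- **Positive/negative status.** Report the exact paired test as descriptive only. Under the r = 0.9 assumptions it reaches two-sided 0.1 in only about 2%, 10%, 13% and 7% of trials at 20%, 40%, 60% and 80% positivity. At 20%, 0.2 × 17 gives about 3 baseline positives; if all 3 turned negative, p = 2 × (1/2)³ = 0.25.
- **ddPCR HIV DNA.** Analyse log10 copies with left-censoring at the limit that applies to the trial assay, and state that limit.

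The cost is plan wording and somewhat more complex models, which may fail to converge with 17 patients, so name the alternative in advance. No new visits, samples or assays are needed. Well counts and cell inputs come from the planned outgrowth assay, but they must be kept as analysis data.
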